#### **STUDY VISITS AND PROCEDURES:**

Inclusion and exclusion qualifications will be assessed at the preoperative visit according to the inclusion/exclusion criteria. The Informed Consent Form and Authorization for Use/Disclosure of Health Information form (HIPAA authorization) must be signed by any patients who agree to participate in the study prior to undergoing any study-specific procedures. Those subjects who meet the inclusion/exclusion criteria and agree to participate will be randomized to receive the same lens model in both eyes: either the test Model ZHR00 IOL or control Model ZCB00 IOL. The eye implanted first will be considered the primary study eye. All subjects are intended to have bilateral cataract surgery with the second-eye surgery occurring after the 1-week exam for the first eye but no more than 30 days after the first-eye surgery. Subjects and study personnel performing the postoperative vision testing and refractions will be masked for the duration of the study.

Key preoperative data include ocular health and history, visual acuities, manifest refraction, keratometry, biomicroscopic slit-lamp findings, ocular symptoms and biometry. The operative visit will include standard procedures for cataract surgery and IOL implantation. Key postoperative data collection includes monocular and binocular uncorrected and distance-corrected visual acuities, contrast sensitivity, defocus curve, slit-lamp findings, non-directed visual symptoms, questionnaires and adverse events.

## 2. BACKGROUND/INTRODUCTION

Presbyopia, defined as the age-related loss of accommodative amplitude, affects essentially all human beings beyond the age of 45 and impacts the ability of the eye to focus at near distances. Current intraocular lens options for cataract patients who desire improved vision across a range of distances include a choice of monovision or multifocality. Patients implanted with standard monofocal lenses often need spectacles for reading or performing other near tasks, even if a monovision option is selected. Patients implanted with multifocal lenses, while being able to read and perform other near tasks without spectacles, sometimes experience dysphotopsias (e.g., halos), particularly at night, and may have limited intermediate ability (e.g., may need spectacles to work on a computer). Some accommodating lenses are also available on the market, although their effect depends upon fit within the capsular bag or capsular bag elasticity.

On July 15, 2016, another option was made available to cataract patients when the TECNIS Symphony Extended Range of Vision IOL, Model ZXR00, became commercially available in the United States. Utilizing a diffractive technology to elongate the depth of focus, the Symphony IOLs provide cataract patients with good distance vision, and improved intermediate and near vision compared to standard monofocal IOLs.

The investigational IOL device in this protocol, Model ZHR00, is an enhanced version of the commercially-available TECNIS Symphony. The diffractive technology on the posterior optic surface of the TECNIS Symphony IOL was modified for the investigational IOL model ZHR00, with the goal of providing improved intermediate vision as compared to the control IOL Model ZCB00.

## 3. CLINICAL HYPOTHESIS

The Next-Generation TECNIS Symphony IOL, Model ZHR00, will provide improved monocular, distance-corrected intermediate visual acuity (at 66 cm) and distance-corrected near visual acuity near (at 40 cm), as well as increased depth of focus at 0.2 LogMAR and increased spectacle independence compared to the control IOL, TECNIS Model ZCB00. Complication and adverse event rates associated with the Next-Generation ZHR00 IOL will be within the rates for posterior chamber IOLs given in ISO 11979-7:2006/ Amd 1:2012(E).

## 4. STUDY DESIGN

This study is a 6-month, prospective, multicenter, subject/evaluator-masked, bilateral, randomized clinical investigation of the Next-Generation TECNIS Symphony IOL Model ZHR00 versus the TECNIS Model ZCB00 IOL.

The study will be conducted at up to 10 sites in the U.S.A and will enroll up to 264 subjects to achieve approximately 220 randomized and bilaterally-implanted subjects, resulting in approximately 100 evaluable subjects in each lens group at 6 months. Subjects are to be implanted with the same IOL in both eyes: the investigational ZHR00 IOL, or the control ZCB00 IOL. The eye implanted first will be considered the primary study eye.

## 5. ACRONYMS

The following acronyms are used throughout this document:

- UCDVA: uncorrected distance visual acuity
- BCDVA: best-corrected distance visual acuity
- UCIVA: uncorrected intermediate visual acuity
- DCIVA: distance-corrected intermediate visual acuity
- UCNVA: uncorrected near visual acuity
- DCNVA: distance-corrected near visual acuity
- D: diopters

## 6. STUDY OBJECTIVES AND ENDPOINTS

The purpose of this study is to evaluate the safety and effectiveness of the Next-Generation TECNIS Model ZHR00 IOL. The key study timeframe for all endpoints will be the 6-month postoperative visit. Data for other visits will be included in the final analysis, but no interim analysis will be conducted.

### 6.1 PRIMARY EFFECTIVENESS ENDPOINTS

#### MONOCULAR, PHOTOPIC DCIVA AT 66 CM

Success criteria:

- Statistically significant improvement in mean distance-corrected intermediate visual acuity for the ZHR00 eyes vs. control eyes
- The median DCIVA of the ZHR00 lens group is at least 0.2 LogMAR

#### MONOCULAR, DISTANCE-CORRECTED DEFOCUS CURVE

Success criteria: The Model ZHR00 lens demonstrates at least 0.5 D greater monocular, photopic, distance-corrected depth of focus compared to the control IOL at 0.2 LogMAR visual acuity threshold, based on visual inspection of the defocus curves.

### 6.2 SECONDARY EFFECTIVENESS ENDPOINTS

#### MONOCULAR, PHOTOPIC DCNVA AT 40 CM

Success criteria:

- Statistically significant improvement in mean LogMAR distance-corrected near visual acuity for ZHR00 eyes vs. control eyes
- The median DCNVA of the ZHR00 lens group is at least 0.3 LogMAR

#### OVERALL SPECTACLE INDEPENDENCE

Success criteria:

- Statistically significantly greater proportion of subjects in the ZHR00 group who are spectacle independent, as determined from PRO instrument assessing need for correction, use of correction and ability to see without strain. Clinical significance will be determined as follows:
  - The proportion of Model ZHR00 subjects who are spectacle independent will be at least 25 percentage points higher than that for the control group

### **6.3 SAFETY ENDPOINTS**

#### MONOCULAR BCDVA

Success criteria: The mean BCDVA for the ZHR00 eyes will be statistically non-inferior to that of the control ZCB00 IOL group using a non-inferiority margin of 0.1 LogMAR.

#### ADVERSE EVENT RATE

Rates of adverse events for the ZHR00 eyes vs. ISO SPE rates. Adverse events will include any lens-related secondary surgical intervention due to optical issues causing visual symptoms.

#### CONTRAST SENSITIVITY

Monocular best-corrected distance contrast sensitivity (mesopic with and without glare at 1.5, 3, 6, and 12 cpd photopic with glare at 3, 6, 12, and 18 cpd) will be summarized by descriptive statistics for each IOL group.

#### VISUAL SYMPTOMS VIA PRO INSTRUMENT

Visual symptoms, as reported and rated via the Patient Reported Visual Symptoms Questionnaire (PRVSQ), will be summarized by frequency and percentage for each IOL group.

### **6.4 OTHER ENDPOINTS**

- Monocular BCDVA percent 20/40 or better vs. ISO SPE rate
- Binocular best-corrected distance depth of focus

- Binocular UCDVA, UCIVA, and UCNVA
- Monocular UCDVA, UCIVA, and UCNVA
- Monocular, first-eye, low-contrast DCIVA and BCIVA (10%)
- Medical findings/complications
- Lens findings/complications
- Fundus visualization
- Residual refractive error
- Ocular/visual symptoms (non-directed responses as obtained from the open-ended question “Are you having any difficulties with your eyes or vision?”)
- Subject satisfaction and other questionnaire responses

## 7. STUDY PRODUCTS

### 7.1 INTRAOCULAR LENSES

The two lens models used in this study are the investigational Next-Generation TECNIS Symphony IOL, Model ZHR00, and the control TECNIS Monofocal IOL, Model ZCB00. The investigational IOL is a modification of the TECNIS Symphony IOL, which is a single-piece, SENSAR acrylic IOL with a modified prolate (aspheric) design on the anterior optic surface to reduce spherical aberration and a diffractive posterior optic design.

#### Investigational TECNIS IOL Model ZHR00

The TECNIS IOL Model ZHR00 is a posterior chamber, 1-piece, aspheric, diffractive, acrylic, foldable IOL designed for placement in the capsular bag (**Figure 1**). The lens is made of the same hydrophobic SENSAR acrylic material as the material/mechanical 1-piece parent, the JJSV SENSAR 1 Piece IOL, Model AAB00, and the optical parent TECNIS Symphony IOL, Model ZXR00 (**Figure 2**). The ZHR00 lens has the same overall geometry/dimensions (13 mm overall length and 6 mm optic diameter) as the material/mechanical 1-piece parent IOL, the JJSV SENSAR IOL, Model AAB00, and the optical parent, TECNIS Symphony IOL, Model ZXR00. The investigational ZHR00 lens also has the same TECNIS modified prolate (aspheric) design on the anterior optic surface as the optical parent, the TECNIS Symphony IOL, to reduce spherical aberration.

The Model ZCB00 control IOL (**Figure 3**) shares the same lens material, general dimensions, lens geometry, and one-piece soft acrylic lens platform as the SENSAR 1-Piece IOL, Model AAB00, which is the material/mechanical parent of the ZHR00 IOL.

The posterior optic design of the ZHR00 lens has been modified from that of the optical parent IOL, model ZXR00. The modifications to the posterior diffractive optics of the investigational IOL are designed to further extend the depth of focus compared to the TECNIS Symphony IOL.

Figure 1: Drawing and Photograph of a TECNIS Model ZHR00 IOL

[figure not shown]

Figure 2: Drawing and Photograph of a TECNIS Symphony IOL

[figure not shown]
[figure not shown]

Figure 3: Drawing and Photograph of a TECNIS IOL, Model ZCB00

Like all of JJSV's 1-piece soft acrylic IOLs, investigational IOL Model ZHR00, TECNIS Symphony IOL Model ZXR00, and the TECNIS IOL Model ZCB00 have a surface treatment of Polyethylene Glycol (PEG) to reduce tackiness of the lens surface and include a ProTEC 360° barrier edge, the stability of Tri-Fix 3-point design, and a frosted-edge treatment.

#### INDICATIONS FOR INVESTIGATIONAL IOL

The Model ZHR00 is currently indicated for primary implantation for the visual correction of aphakia, in adult patients with less than 1 diopter of preexisting corneal astigmatism, in whom a cataractous lens has been removed. The lens mitigates the effects of presbyopia by providing an extended depth of focus. Compared to an aspheric monofocal IOL, the lens provides improved intermediate and near visual acuity, while maintaining comparable distance visual acuity. The Model ZHR00 IOL is intended for capsular bag placement only.

#### INDICATIONS FOR CONTROL IOL

The TECNIS monofocal IOL Model ZCB00 is indicated for the visual correction of aphakia in adult patients in whom a cataractous lens has been removed by extracapsular cataract extraction. These devices are intended to be placed in the capsular bag.

#### STORAGE AND DISTRIBUTION

Consignments of the investigational study lens models will be supplied to the investigative sites. All study lenses should be stored in the original packaging and kept in a dry place. Lenses should not be stored in direct sunlight or at temperatures greater than 45° C (113°F). Each lens is packaged in a lens tray and sealed in a peel-pouch. The lens is sterile as long as the package has not been opened or damaged and the shelf-life expiration date has not been exceeded. The Principal Investigator is responsible for ensuring that the investigational lenses are used only for subjects enrolled in this study.

#### COMPARISON CHART

**Table 1** describes the dimensional and optical similarities between the study lenses and other associated JJSV lenses.

Table 1: Comparison of Design Features

	SENSAR 1-PIECE IOL MODEL AAB00 (MECHANICAL/MATERIAL PARENT)	TECNIS 1-PIECE IOL MODEL ZCB00 (MONOFOCAL ANALOG)	TECNIS SYMFONY EXTENDED RANGE OF VISION IOL MODEL ZXR00 (OPTICAL PARENT)	MODEL ZHR00 (SUBJECT DEVICE)
LENS DESIGN	1-piece acrylic monofocal with spherical anterior surface	1-piece acrylic monofocal with aspheric anterior surface	1-piece acrylic extended range of vision IOL with aspheric anterior surface	1-piece acrylic extended range of vision IOL with aspheric anterior surface
LENS MATERIAL	Surface-treated SENSAR® soft acrylic material	Same as AAB00	Same as AAB00	
DIMENSIONAL FEATURES				
OVERALL DIAMETER	13.0 mm	Same as AAB00	Same as AAB00	
OPTICAL CENTER THICKNESS	0.74 mm (20 D lens)	0.72 mm (20 D lens)	0.66 mm	Same as ZXR00
HAPTIC ANGLE	No angulation, but offset from optic body	Same as AAB00	Same as AAB00	
OPTIC BODY DIAMETER	6.0 mm	Same as AAB00	Same as AAB00	
HAPTIC MATERIAL	Same as optic	Same as AAB00	Same as AAB00	
HAPTIC WIDTH	0.39 mm	Same as AAB00	Same as AAB00	
HAPTIC THICKNESS	0.46 mm	Same as AAB00	Same as AAB00	
HAPTIC STYLE	C-Loop	Same as AAB00	Same as AAB00	
OPTICAL FEATURES				
OPTIC SHAPE	Biconvex	Same as AAB00	Same as AAB00	
ANTERIOR OPTIC PROFILE	Spherical	Aspheric	Same as ZCB00	
POSTERIOR OPTIC PROFILE	Spherical monofocal	Same as AAB00	Diffractive extended range of vision	Same as ZXR00
OPTIC EDGE DESIGN	PROTEC squared edge	Same as AAB00	Same as AAB00	
DIOPTRIC POWER RANGE	+6.0 to +30.0D in 0.5D increments	+5.0 to +34.0D in 0.5D increments 	Same as ZCB00 	
REFRACTIVE INDEX	1.470 (35° C)	Same as AAB00	Same as AAB00	
ADD POWER	N/A	N/A	N/A 	N/A 
RANGE OF VISION	N/A	N/A	Through 2.0 D 	Through 3.0 D 

 Only IOLs from +14.0 D to +26.0 D will be used in the clinical study.

 There is no distinct add power. Clinically, the range of the defocus with binocular visual acuity above 0.2 LogMAR is approximately 2.0 D in the near direction.

 There is no distinct add power.

## 7.2 IOL IMPLANTATION SYSTEMS

The investigational TECNIS IOL Model ZHR00 and the control TECNIS IOL Model ZCB00 lenses are to be implanted using the UNFOLDER Platinum 1 Series Implantation System (DK7796 handpiece with the UNFOLDER Platinum 1 Series cartridge, Model 1MTEC30) or the ONE SERIES Ultra Implantation System (DK7786 or DK7791 handpiece with the One Series Ultra cartridge, Model 1VIPR30).

## 8. STUDY POPULATION

All study subjects will be enrolled from the normal surgical cataract population at up to 10 sites in the U.S.A. Up to 264 subjects will be enrolled to achieve approximately 220 randomized and bilaterally implanted subjects, resulting in at least 200 evaluable subjects (a minimum of 100 in each test and control groups) at 6 months. This allows for a screen failure rate of approximately 15% and a drop-out rate of approximately 10% for implanted subjects. Each site should implant a minimum of 20 subjects, and no site may implant more than 25% of the enrollment total.

This study will include only subjects undergoing bilateral primary cataract extraction and IOL implantation and who meet all of the study inclusion and exclusion criteria in both eyes. All subjects who meet the eligibility criteria will be offered enrollment in the study. Eligibility criteria may not be waived by the investigator. Any questions regarding patient eligibility are to be discussed with JJSV prior to subject enrollment. Those subjects who meet the eligibility criteria and agree to participate will be randomized to receive either the Model ZHR00 or Model ZCB00 control IOLs in both eyes. Subjects will be enrolled at each site sequentially until the overall study recruitment goals are met or the site limit is reached.

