### **STUDY POPULATION CHARACTERISTICS:**

**Condition:** Bilateral cataracts with otherwise-healthy eyes

**Number of Subjects:** Up to 264 subjects will be enrolled to achieve approximately 110 randomized and bilaterally-implanted subjects in each lens group.

Each site should enroll at least 20 subjects, and no site may enroll more than 25% of the enrollment total.

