## **10. EXPERIMENTAL PLAN**

### **10.1 OVERVIEW**

This study will be conducted in accordance with U.S. Code of Federal Regulations, the Declaration of Helsinki, ISO 14155:2011 and all other applicable laws and regulations. The study will not begin until regulatory and IRB approvals have been obtained.

This study will be a prospective, multicenter, bilateral, randomized, comparative subject/evaluator-masked clinical investigation conducted at up to 10 sites. Up to 264 subjects will be enrolled to achieve approximately 220 randomized and bilaterally implanted subjects, resulting in a minimum of 200 evaluable subjects (approximately 100 in each test and control groups) at 6 months. After informed consent is obtained and confirmation that all eligibility criteria are met, the eye(s) may be treated.

After signing the informed consent form, subjects meeting all eligibility criteria will be randomized to receive lenses from the same lens group in both eyes: either the investigational Model ZHR00 or the Model ZCB00 control IOL. For each subject, the investigator will choose which eye to operate on first at his/her discretion based on his/her standard clinical practice (e.g., the eye with the worse cataract, poorer best-corrected distance vision and/or more severe optical/visual complaints). All subjects are intended to have bilateral cataract surgery with the second-eye surgery occurring after the 1-week postoperative exam for the first eye, but no more than 30 days after the first-eye surgery. All subjects will be examined through 6 months postoperatively according to the visit schedule described in Section 10.2, Visit Schedule.

Although the investigators implanting the lenses cannot be masked, subjects and study evaluators responsible for conducting all vision testing will remain masked to which lenses were implanted through the 6-month study visit. Because differences between

the investigative and control lenses may be discernible upon slit-lamp examination, special care must be taken to maintain masking of study technicians. As such, it is recommended that only the investigator, sub-investigator or other designated and trained clinician perform all biomicroscopic slit-lamp exams. To maintain consistency, as well as masking, it is recommended that a single individual (study technician or coordinator designated by the investigator) conduct all postoperative study-related vision testing, although a back-up person should also be designated and trained.

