## **20.7 SAMPLE SIZE CALCULATIONS**

For the primary endpoint of distance-corrected intermediate visual acuity, there is more than 90% power to detect a 1-line or greater difference in mean visual acuity between

the investigational lens and the control groups (assume one-sided testing with an alpha of 0.025 and standard deviation of 1.6 lines) with 100 subjects in each lens group.

For the secondary endpoint of distance-corrected near visual acuity, there is more than 90% power to detect a 1-line or greater difference in mean visual acuity between the investigational lens and the control groups (assume one-sided testing with an alpha of 0.025 and standard deviation of 1.6 lines) with 100 subjects in each lens group.

Accounting for a potential 15% screen failure and 10% loss-to-follow-up rate, the study will enroll up to 264 subjects.

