## 1 INTRODUCTION

This document summarizes the statistical methods to be implemented during the analysis of data for the TECNIS® 1-Piece aspheric acrylic intraocular lens (IOL), Model ZHR00 (SUR-IOL-652-2001) study. This study will be a 6-month, prospective, multicenter, bilateral, subject/evaluator-masked, randomized clinical trial conducted at up to 10 sites. Subjects will be bilaterally implanted with either the Model ZHR00 IOL or the control Model ZCB00 IOL. Up to 264 subjects will be enrolled to achieve approximately 224 subjects randomized and bilaterally implanted, resulting in approximately 200 evaluable subjects (100 in the study arm and 100 in the control arm) at 6 months.

The key time point for reporting and submitting the PMA supplement will be at 6 months. The primary effectiveness endpoints for this study are mean (LogMAR) monocular distance corrected intermediate visual acuity (DCIVA) under photopic conditions, at a fixed distance (66 cm) and monocular distance-corrected defocus curve at 6-months postoperative.

The secondary effectiveness endpoints are mean (LogMAR) monocular distance corrected near visual acuity (DCNVA) at 40 cm, and overall spectacle independence at 6-months postoperative.

The safety endpoints are monocular best corrected distance visual acuity (BCDVA) non-inferior to control, the rates of adverse events compared to ISO 11979-7 SPE (safety and performance endpoints) including SSI due to optical issues causing visual symptoms, contrast sensitivity and visual symptoms via PRO questionnaire evaluated at 6 months.

Other key endpoints include binocular defocus curve testing, other visual acuity, refractive data, medical findings, lens findings, ocular/visual symptoms (non-directed), fundus visualization, subject satisfaction and other questionnaire responses.

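### Does the protocol's figure of about 220 implanted subjects, against the SAP's 224, leave the trial short of 100 evaluable per group?

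*Protocol*

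**What the plan says.** The protocol gives the implanted count as about 220 throughout. The Synopsis has "approximately 110 randomized and bilaterally-implanted subjects in each lens group". Section 4 has "approximately 220 randomized and bilaterally-implanted subjects, resulting in approximately 100 evaluable subjects in each lens group at 6 months". Section 8 has "approximately 220 randomized and bilaterally implanted subjects, resulting in at least 200 evaluable subjects (a minimum of 100 in each test and control groups"), with a screen failure rate of roughly 15% and "a drop-out rate of approximately 10% for implanted subjects". Section 10.1 repeats the 220, "resulting in a minimum of 200 evaluable subjects (approximately 100 in each test and control groups) at 6 months". Section 20.7 closes with "Accounting for a potential 15% screen failure and 10% loss-to-follow-up rate, the study will enroll up to 264 subjects".

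The SAP uses 224. Its Section 1 reads "Up to 264 subjects will be enrolled to achieve approximately 224 subjects randomized and bilaterally implanted". The same section then describes the expected yield as "resulting in approximately 200 evaluable subjects (100 in the study arm and 100 in the control arm) at 6 months". Section 7.4 shows the derivation: 200 evaluable, inflated for 10% drop-out and then for 15% screen failure, with rounding to 224 and 264. The opening of SAP Section 7 gives the reason for the target: the draft standard for extended-depth-of-focus lenses requires at least 100 bilaterally implanted evaluable subjects per lens group.

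**The concern.** Within one paragraph, Section 8 states an implanted count, a loss rate and a minimum that do not fit together if all three are read as exact. The SAP's own derivation suggests which number is out of line. The protocol keeps the 264 that the SAP chain produces but pairs it with 220, which that chain does not produce.

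The minimum matters because SAP Section 7 bases the sample size on the draft standard's 100 evaluable per group and not on power. Ample power would therefore not excuse a shortfall. The wording of the target also varies: a minimum in total and per group (Protocol Section 8), a minimum in total but about 100 per group (Section 10.1), about 100 per group (Section 4) and about 200 in total (SAP Section 1). A reader could ask whether 99 in one group would satisfy the plan.

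**Working it through.** **Inputs.** Target of 200 evaluable, 100 per group (Protocol Section 8; SAP Sections 1 and 7.4). Drop-out 10% and screen failure 15% (Protocol Sections 8 and 20.7; SAP Section 7.4). Enrolment cap 264 (both documents). For power: a difference of 1 line, SD 1.6 lines, one-sided alpha 0.025 (Protocol Section 20.7; SAP Section 7.1).

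**1. Reproducing the SAP figures**, with N / (1 − rate):
- Randomized: 200 / 0.90 = 222.2. Per group, 100 / 0.90 = 111.1, rounded up to 112, and 2 × 112 = 224.
- Enrolled: 224 / 0.85 = 263.5, rounded up to 264.

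Both SAP numbers reproduce.

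**2. Expected evaluable subjects**, with N × (1 − 0.10):

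| Implanted | Evaluable, total | Evaluable, per group |
|---|---|---|
| 220 | 198.0 | 99.0 |
| 224 | 201.6 | 100.8 |

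**3. Rates implied by the protocol's chain:**
- 264 to 220: 1 − 220/264 = 16.7% screen failure, against about 15% stated. For 264 to 224 it is 15.2%.
- 220 to 200: 1 − 200/220 = 9.1% drop-out, against about 10% stated. For 224 to 200 it is 10.7%.

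The protocol's chain is thus met with rates of 16.7% and 9.1%, each within two percentage points of a rate given as approximate.

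**4. Yield of the cap.** 264 × 0.85 = 224.4 implanted, and 224.4 × 0.90 = 202.0 evaluable. The cap is the same in both documents and supports the minimum at the stated rates.

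**5. Effect on power** for distance-corrected intermediate acuity (noncentral t, effect size 1/1.6 = 0.625, noncentrality 0.625 × √(n/2)):
- n = 99 per group: noncentrality 4.397, power 0.9921.
- n = 100 per group: noncentrality 4.419, power 0.9926.

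Both exceed the 90% claimed. The near-acuity endpoint has the same assumptions, so the same figures apply.

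**6. What moving to 224 would secure.** Assume, for illustration only, that subjects drop out independently at exactly 10% and that implantation stops at exactly the stated number. The chance of at least 200 evaluable in total is then 38% from 220 and 69% from 224. The chance that both groups reach 100 is 21% from 110 per group and 45% from 112 per group.

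**The case for a change.** The best argument for a change is that the word for approximately is attached to the 220 and to the two rates, but not to Section 8's minimum of 200 and 100 per group, nor to Section 10.1's minimum of 200. A hard minimum should follow from the inputs beside it, and at 10% it does not. Section 8 also says that sites enrol until the overall recruitment goals are met, so the goal ought to be one number. The illustration in step 6 favours 224.

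Part of this stands. The protocol and the SAP do give different counts, and if implantation stopped at exactly 220 and drop-out were exactly 10%, the total would be 198.

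The rest does not carry a change. A shortfall of two appears only when two approximate figures are treated as exact and set against a firm one; 224 to the nearest ten is 220. Step 6 assumes that 220 or 224 is a fixed stopping point, which neither document says. Even on that assumption, 224 leaves less than an even chance that both groups reach 100, so substituting the number would not guarantee the minimum. What decides it is the drop-out that occurs.

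On the status of the 100, the passages that set the requirement agree: Section 8 and SAP Section 7 both call it a minimum. The softer wording in Sections 4 and 10.1 and in SAP Section 1 is overview text describing the expected yield, and does not set a competing requirement.

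**Conclusion.** The arithmetic behind the concern is right, and the plan needs no change. The protocol's 220 is a rounded planning figure where the SAP shows the derivation and reaches 224. The gaps are 4 implanted subjects (4/224 = 1.8%) and, at exactly 10% drop-out, 2 evaluable subjects out of 200 (1.0%). The enrolment cap, the rates and the minimum of 100 per group that justifies the sample size are common ground. The cap yields about 202 evaluable subjects at those rates. Power moves from 99.3% to 99.2% between 100 and 99 per group, and no analysis, population or success criterion uses 220 or 224.

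This rests on reading 220 as the approximate figure the protocol calls it, on recruitment being free to run up to 264, and on screen failure and drop-out near 15% and 10%. If losses were clearly higher, both counts would miss the minimum: 224 fails in expectation once drop-out passes 10.7%, and 220 once it passes 9.1%. The mismatch is a clerical slip, and correcting it would alter nothing in the conduct or conclusions of the trial.
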